6.2 Definitions of serious adverse event

A serious adverse event is an AE occurring during any study phase, that fulfils one or more of the following criteria:

- Results in death
- Is immediately life-threatening
- Requires in-patient hospitalization or prolongation of existing hospitalization
- Results in persistent or significant disability or incapacity
- Is a congenital abnormality or birth defect
- Is an important medical event that may jeopardize the subject or may require medical intervention to prevent one of the outcomes listed above.

For further guidance on the definition of a SAE, see [Appendix A](#) to the Clinical Study Protocol.

6.3 Recording of adverse events

6.3.1 Time period for collection of adverse events

Adverse Events (including SAEs) will be collected from the time of informed consent, throughout the treatment period and including the EOS visit.

6.3.2 Follow-up of unresolved adverse events

Any AEs that are unresolved at the patient's last AE assessment (EOS) or other assessment / visit as appropriate in the study are followed up by the Investigator for as long as medically

indicated, but without further recording in the eCRF. AstraZeneca retains the right to request additional information for any patient with ongoing AE(s)/SAE(s) at the end of the study, if judged necessary.

6.3.3 Variables

The following variables will be collect for each AE;

- AE (verbatim)
- The date when the AE started and stopped
- Maximum intensity
- Whether the AE is serious or not
- Investigator causality rating against the Investigational Product (yes or no)
- Action taken with regard to investigational product
- Outcome.

In addition, the following variables will be collected for SAEs:

- Date AE met criteria for serious AE
- Date Investigator became aware of serious AE
- AE is serious due to
- Date of hospitalization
- Date of discharge
- Probable cause of death
- Date of death
- Autopsy performed
- Causality assessment in relation to Study procedure(s)
- Causality assessment to other medication
- Description of AE.

Intensity rating scale:

- 1 mild (awareness of sign or symptom, but easily tolerated)
- 2 moderate (discomfort sufficient to cause interference with normal activities)
- 3 severe (incapacitating, with inability to perform normal activities)

It is important to distinguish between serious and severe AEs. Severity is a measure of intensity whereas seriousness is defined by the criteria in Section 6.2. An AE of severe

intensity need not necessarily be considered serious. For example, nausea that persists for several hours may be considered severe nausea, but not a SAE unless it meets the criteria shown in Section 6.2. On the other hand, a stroke that results in only a limited degree of disability may be considered a mild stroke but would be a SAE when it satisfies the criteria shown in Section 6.2.

6.3.4 Causality collection

The Investigator will assess causal relationship between Investigational Product and each Adverse Event, and answer ‘yes’ or ‘no’ to the question ‘Do you consider that there is a reasonable possibility that the event may have been caused by the investigational product?’

For SAEs causal relationship will also be assessed for other medication and study procedures. Note that for SAEs that could be associated with any study procedure the causal relationship is implied as ‘yes’.

A guide to the interpretation of the causality question is found in [Appendix A](#) to the Clinical Study Protocol.

6.3.5 Adverse events based on signs and symptoms

All AEs spontaneously reported by the patient or care provider or reported in response to the open question from the study site staff: ‘Have you had any health problems since the previous visit?’, or revealed by observation will be collected and recorded in the eCRF. When collecting AEs, the recording of diagnoses is preferred (when possible) to recording a list of signs and symptoms. However, if a diagnosis is known and there are other signs or symptoms that are not generally part of the diagnosis, the diagnosis and each sign or symptom will be recorded separately.

6.3.6 Adverse events based on examinations and tests

The results from the Clinical Study Protocol mandated laboratory tests and vital signs will be summarised in the Clinical Study Report (CSR). Deterioration as compared to baseline in protocol-mandated laboratory values, vital signs should therefore only be reported as AEs if they fulfil any of the SAE criteria or are the reason for discontinuation of treatment with the investigational product.

If deterioration in a laboratory value/vital sign is associated with clinical signs and symptoms, the sign or symptom will be reported as an AE and the associated laboratory result/vital sign will be considered as additional information. Wherever possible the reporting Investigator uses the clinical, rather than the laboratory term (e.g., anaemia versus low haemoglobin value). In the absence of clinical signs or symptoms, clinically relevant deteriorations in non-mandated parameters should be reported as AE(s).

Any new or aggravated clinically relevant abnormal medical finding at a physical examination as compared with the baseline assessment will be reported as an AE.

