2. STUDY OBJECTIVES

2.1 Primary objective

Primary Objective:	Outcome Measure:
Maintenance Phase To assess open-label, long-term (12 months) safety and tolerability for ZS in Japanese subjects with hyperkalemia (serum potassium ≥ 5.1 mmol/L).	Safety and tolerability as measured by adverse events reporting, vital signs, ECGs, physical examinations, and safety laboratory measurements.

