3.11 Interruption of investigational product

Investigational product (IP) may be interrupted in situations such as an adverse event, laboratory abnormality other than potassium abnormality (only during Maintenance Phase) at the investigator's discretion.

During an interruption of IP, the patient will return to the site at least every 7 (\pm 2) days as an extra visit for a potassium measurement and recording of any adverse events and concomitant medications (Patient will arrive at the clinic in the morning after fasting for at least 8 hours prior to potassium sample collection.). In case it is unlikely to re-start IP, patient should be discontinued from the IP. On each extra visit, investigator and sponsor should discuss the study continuation. When the patient re-start IP, dose should be the same as the last dose before interruption. If the IP was interrupted due to an AE, the causality of the AE must be judged by investigator to be not related to IP upon resuming the IP.

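### Section 6.3.6 makes a scheduled laboratory deterioration an AE only if it is serious or stops ZS for good, so a symptom-free one that only interrupts ZS under section 3.11 leaves no AE record

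*Protocol*

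**What the plan says.** The primary outcome in section 2.1 is "Safety and tolerability as measured by adverse events reporting, vital signs, ECGs, physical examinations, and safety laboratory measurements". AE reporting is named first, but laboratory results and vital signs are components in their own right.

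Section 6.3.6 explains that results of the scheduled tests will be summarised in the study report. From this it concludes that deteriorations in them "should therefore only be reported as AEs if they fulfil any of the SAE criteria or are the reason for discontinuation of treatment". If such a deterioration comes with signs or symptoms, the sign or symptom is an AE. A clinically relevant deterioration in a parameter that the protocol does not schedule is to be reported as an AE even without symptoms.

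Section 3.11 says that the product "may be interrupted in situations such as an adverse event, laboratory abnormality other than potassium abnormality", with a bracket limiting this to the Maintenance Phase. It keeps interruption distinct from stopping for good: "In case it is unlikely to re-start IP, patient should be discontinued from the IP". For resumption it adds: "If the IP was interrupted due to an AE, the causality of the AE must be judged by investigator to be not related to IP".

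Section 6.3.3 lists the variables collected for each AE. They include maximum intensity, the investigator's causality rating and "Action taken with regard to investigational product".

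**The concern.** Section 6.3.6 relies on the scheduled results being tabulated elsewhere and lifts them into AE reporting only when they have a serious outcome or change treatment. When it was written, the treatment change that it had to name was discontinuation. Version 5.0 added interruption as a second possible consequence and named a laboratory abnormality as a ground for it. The version history lists no matching change to 6.3.6.

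The result is a class of events that the investigator considered important enough to withhold ZS for, yet which the reporting rule keeps out of the AE data. In a single-arm study whose primary objective is long-term safety and tolerability, no comparison group shares the omission. The laboratory tables show the values. They do not show that drug was withheld because of them, or whether the investigator thought the change was related to ZS.

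**Working it through.** The point is textual, so the check is to follow one kind of event through the sections. Take a deterioration in a scheduled laboratory test, for example magnesium, phosphate, calcium or creatinine, during the Maintenance Phase.

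1. It meets a seriousness criterion in 6.2, which includes important medical events: AE under 6.3.6.
2. It is the reason for discontinuing ZS, at once or after an interruption from which restart became unlikely: AE under 6.3.6.
3. It comes with a sign or symptom: the sign or symptom is an AE under 6.3.6, and the laboratory value is supporting information.
4. It is non-serious and symptom-free, and ZS is interrupted under 3.11 and later restarted: neither condition in 6.3.6 is met, so there is **no AE**.
5. For comparison, a clinically relevant, symptom-free deterioration in a test that the protocol does not schedule: AE under 6.3.6, whatever happens to treatment.

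What case 4 loses, section by section:

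- Sections 6.3.3 and 6.3.4 attach intensity, causality and action taken to each AE. Without an AE record the protocol specifies none of these for the event.
- Section 8.5.2 reports type, incidence, timing, relationship and severity of treatment-emergent and serious AEs. Case 4 enters none of these tables.
- Section 7.5 requires drug administration to be recorded in the case report form, but does not mention a reason for interruption.
- The causality condition for restart in 3.11 is worded for interruptions due to an AE. Read with 6.3.6, it does not attach to case 4. Whether a causality judgement is needed on restart then depends on a reporting convention.

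What case 4 keeps: its values are in the laboratory component of the primary outcome. Section 8.5.2 names the incidence of hypokalemia, hypomagnesemia, hypophosphatemia and hypocalcemia among the safety endpoints and also covers creatinine, eGFR, bilirubin, AST and ALT.

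Size: the protocol gives no rate of laboratory-driven interruption, so the number of patients in case 4 cannot be computed. Only the weight of one patient can be shown. The synopsis plans 150 patients entering the Correction Phase and approximately 100 treated for a year. Interruption for a laboratory abnormality applies only in the Maintenance Phase, which not all 150 will reach, so 150 is an upper bound on the denominator. One affected patient with no other AE lowers AE incidence by 1/150 = 0.67 percentage points with 150 patients, or 1/100 = 1.0 point if the denominator were as low as 100. A patient who has another AE changes event counts but not the proportion with any AE.

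**The case against.** The strongest reply is that 6.3.6 is a deliberate convention with its reason stated: scheduled results are tabulated, so they need not also be AEs. Section 3.11 lists a laboratory abnormality separately from an adverse event, which fits that convention, so the two sections do not contradict each other. This stands as far as it goes. A reader might infer a direct contradiction, but the sections can both be followed; together they leave a gap.

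A reader might also infer that these abnormalities vanish from the primary safety outcome. The documents do not support that, because laboratory measurements are themselves part of the outcome and are summarised. Nor is every laboratory-driven interruption lost, since symptoms, clinically relevant new physical findings and serious events are all AEs. Vital signs are covered by 6.3.6, but 3.11 does not name them as a ground for interruption; they come in only through its open-ended wording.

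Neither are interruptions invisible. Section 3.11 requires extra visits at least every 7 (±2) days and a discussion between investigator and sponsor at each, and dosing is recorded. The case report form is not at hand and may well hold a reason for interruption. Even so, a reason on a dosing page would not supply intensity or causality or enter the AE tables.

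The most substantial objection concerns the remedy. Making these events AEs would bring them under the restart condition in 3.11 and so could affect who may resume ZS. That is correct, and it means 6.3.6 cannot be amended alone.

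**Conclusion.** The gap is real and narrow. As written, a scheduled laboratory deterioration that is non-serious, symptom-free and leads only to interruption of ZS is not an AE. It carries no intensity, causality or action-taken record and is absent from AE and related-AE incidence. The bias runs one way, towards fewer AEs. By the section's own logic, which treats discontinuation as reason enough to report, interruption belongs in the condition.

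The conclusion rests on reading interruption and discontinuation as separate terms, as 3.11 does. It assumes nothing about how often such interruptions occur, and no estimate of that is possible from the protocol. How far related-AE incidence would change after the amendment also depends on 3.11: if its restart condition applies as worded, every such event followed by restart would by then have been judged not related.

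**What to change.** In 6.3.6, extend the second condition so that a deterioration in a scheduled laboratory value or vital sign is an AE if it is the reason for discontinuation or interruption of treatment with the investigational product. Have the record of the interruption point to that AE.

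In the same amendment, reconcile this with the restart sentence in 3.11 and state whether its causality condition is meant to cover laboratory-driven interruptions. Which restart rule is right is a clinical matter on which this review takes no position.

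The cost is a wording change and a note to sites, a few more AE records, a slightly less favourable AE incidence, and the need to settle 3.11 at the same time. The reporting rule would also change while the study is running. Interruption was itself introduced in version 5.0, so interruptions under 3.11 that predate the change can be reviewed and entered by the sites.

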6.4 Reporting of serious adverse events

All SAEs have to be reported, whether or not considered causally related to the investigational product, or to the study procedure(s). All SAEs will be recorded in the Case Report Form (CRF).

If any SAE occurs in the course of the study, then Investigators or other site personnel inform the appropriate AstraZeneca representatives within one day i.e., immediately but **no later than 24 hours** of when he or she becomes aware of it.

The designated AstraZeneca representative works with the Investigator to ensure that all the necessary information is provided to the AstraZeneca Patient Safety data entry site **within 1 calendar day** of initial receipt for fatal and life threatening events **and within 5 calendar days** of initial receipt for all other SAEs.

For fatal or life-threatening adverse events where important or relevant information is missing, active follow-up is undertaken immediately. Investigators or other site personnel inform AstraZeneca representatives of any follow-up information on a previously reported SAE within one calendar day i.e., immediately but **no later than 24 hours** of when he or she becomes aware of it.

Once the Investigators or other site personnel indicate an AE is serious in the WBDC system, an automated email alert is sent to the designated AstraZeneca representative.

If the WBDC system is not available, then the Investigator or other study site staff reports a SAE to the appropriate AstraZeneca representative by telephone.

The AstraZeneca representative will advise the Investigator/study site staff how to proceed.

6.5 Overdose

ZS has been given to patients at doses of up to 30 g per day for 1 to 3 days and up to 15 g per day for 11 months. For the purpose of this study, an overdose is defined as more than 30 g per day.

- An overdose with associated AEs is recorded as the AE diagnosis/symptoms on the relevant AE modules in the CRF and on the Overdose CRF module.
- An overdose without associated symptoms is only reported on the Overdose CRF module.

If an overdose on ZS occurs in the course of the study, then the Investigator or other site personnel inform appropriate AstraZeneca representatives immediately, or **no later than 24 hours** of when he or she becomes aware of it.

The designated AstraZeneca representative works with the Investigator to ensure that all relevant information is provided to the AstraZeneca Patient Safety data entry site.

For overdoses associated with a SAE, the standard reporting timelines apply, see Section 6.4. For other overdoses, reporting must occur within 30 days.

6.6 Pregnancy

All pregnancies and outcomes of pregnancy should be reported to AstraZeneca except for:

- If the pregnancy is discovered before the study subject has received any study drug

6.6.1 Maternal exposure

If a patient becomes pregnant during the course of the study investigational product should be discontinued immediately.

Pregnancy itself is not regarded as an adverse event unless there is a suspicion that the investigational product under study may have interfered with the effectiveness of a contraceptive medication. Congenital abnormalities/birth defects and spontaneous miscarriages should be reported and handled as SAEs. Elective abortions without complications should not be handled as AEs. The outcome of all pregnancies (spontaneous miscarriage, elective termination, ectopic pregnancy, normal birth or congenital abnormality) should be followed up and documented even if the subject was discontinued from the study.

If any pregnancy occurs in the course of the study, then the Investigator or other site personnel informs the appropriate AstraZeneca representatives within 1 day i.e., immediately but **no later than 24 hours** of when he or she becomes aware of it.

The designated AstraZeneca representative works with the Investigator to ensure that all relevant information is provided to the AstraZeneca Patient Safety data entry site within 1 or 5 calendar days for SAEs (see Section 6.4) and within 30 days for all other pregnancies.

The same timelines apply when outcome information is available.

When the CRF module is used include the following: The PREGREP module in the CRF is used to report the pregnancy and the PREGOUT is used to report the outcome of the pregnancy.

6.6.2 Paternal exposure

Nonclinical data with ZS based on conventional studies of safety pharmacology, repeated dose toxicity, genotoxicity, and carcinogenic potential and toxicity to reproduction and development did not reveal special hazard effect on libido, fertility, or embryofetal and postnatal development (see Investigator's Brochure [IB] for further details). Therefore there is no restriction on fathering children or donating sperm during the study.

In case of pregnancy of the patient's partners, an ICF FOR PREGNANT PARTNERS OF STUDY PATIENTS the partner's pregnancy will be sent to the partner to obtain her consent for collection of pregnancy information. Such pregnancy report will follow the same timeframe and routing as described for any participant's pregnancy. These pregnancies will be also followed up, and the

outcome of the pregnancy (spontaneous miscarriage, elective termination, ectopic pregnancy, normal birth or congenital abnormality) should be obtained and documented if possible.

6.7 Medication Error

For the purposes of this clinical study a medication error is an unintended failure or mistake in the treatment process for an AstraZeneca study drug that either causes harm to the patient or has the potential to cause harm to the patient.

A medication error is not lack of efficacy of the drug, but rather a human or process related failure while the drug is in control of the study site staff or patient.

Medication error includes situations where an error.

- occurred
- was identified and intercepted before the patient received the drug
- did not occur, but circumstances were recognize that could have led to an error

Examples of events to be reported in clinical studies as medication errors:

- Drug name confusion
- Dispensing error e.g. medication prepared incorrectly, even if it was not actually given to the patient
- Drug not administered as indicated, for example, wrong route or wrong site of administration
- Drug not taken as indicated e.g. tablet dissolved in water when it should be taken as a solid tablet
- Drug not stored as instructed
- Wrong patient received the medication (excluding IVRS/IWRS errors)
- Wrong drug administered to patient (excluding IVRS/IWRS errors)

Examples of events that **do not** require reporting as medication errors in clinical studies:

- Errors related to or resulting from IVRS/IWRS - including those which lead to one of the above listed events that would otherwise have been a medication error
- Patient accidentally missed drug dose(s) e.g. forgot to take medication
- Accidental overdose (will be captured as an overdose)
- Patient failed to return unused medication or empty packaging
- Errors related to background and rescue medication, or standard of care medication in open label studies, even if an AZ product

Medication errors are not regarded as AEs but AEs may occur as a consequence of the medication error.

If an medication error occurs in the course of the study, then the Investigator or other site personnel informs the appropriate AstraZeneca representatives within 1 day i.e., immediately but **no later than 24 hours** of when he or she becomes aware of it.

The designated AstraZeneca representative works with the Investigator to ensure that all relevant information is completed within 1 or 5 calendar days if there is an SAE associated with the medication error (see Section 6.4) and within 30 days for all other medication errors.

7. INVESTIGATIONAL PRODUCT AND OTHER TREATMENTS

7.1 Identity of investigational product(s)

Investigational product and strength	Dosage form	Manufacturer
Sodium Zirconium Cyclosilicate (ZS) 2.5 g	Powder for Oral Suspension in a sachet	AstraZeneca
Sodium Zirconium Cyclosilicate (ZS) 5 g	Powder for Oral Suspension in a sachet	AstraZeneca
Sodium Zirconium Cyclosilicate (ZS) 10 g	Powder for Oral Suspension in a sachet	AstraZeneca

7.2 Dose and treatment regimens

Sodium Zirconium Cyclosilicate (ZS) should be administered orally as a suspension in water.

[figure not shown]
Correction Phase: ZS 10g TID for 24, 48 or 72 hours (3, 6 or 9 doses). Patients will enter the Maintenance phase after 24, 48 or 72h if the morning i-STAT potassium is between 3.5 and 5.0 mmol/L, inclusive.

Maintenance Phase: The starting dose is ZS 5 g QD. The ZS dose may be increased in increments of 5 g up to a maximum of 15 g QD or decreased to a minimum of 5 g QOD (or 2.5 g QD) dependent upon i-STAT potassium measurements (see Dose modification rules in Table 6).

Table 6 Dose modification rules:

Current dose	i-STAT Potassium Value (mmol/L)	Dose Adjustment
5g QOD or 2.5 g QD	≤ 2.9 3.0-3.4 3.5-5.0 5.1-6.5 >6.5	Discontinue dosing Discontinue dosing No change 5g QD Discontinue dosing
5g QD	≤ 2.9 3.0-3.4 3.5-5.0 5.1-6.5 >6.5	Discontinue dosing 5g QOD or 2.5 g QD No change 10g QD Discontinue dosing
10g QD	≤ 2.9 3.0-3.4 3.5-5.0 5.1-6.5 >6.5	Discontinue dosing 5g QD No change 15g QD Discontinue dosing
15g QD	≤ 2.9 3.0-3.4 3.5-6.5 >6.5	Discontinue dosing 10g QD No change Discontinue dosing

For subjects who require a lower dose than 5 g QD, the first 75 subjects will have their dose reduced to 5 g QOD if this their potassium values indicate that they need this lower dose at any time during the first 6 months of the maintenance phase, and then be switched to 2.5 g QD for the final Month 6 (Visit 17) to Week 52 (end of treatment), if their potassium values are still such that this lower dose is required. The remaining 75 subjects will receive the reduced dose of 2.5 g QD for the first 6 months (up to Visit 17) of the maintenance phase, and then be switched to 5 g QOD for the final Month 6 (Visit 17) to Week 52 (end of treatment), if a their potassium values confirm that a lower dose is still required.

Any time the ZS dose is adjusted, the subject will return to the site 7 (\pm 2) days later as an extra visit for a potassium measurement and recording of any adverse events and concomitant medications (Subjects will arrive at the clinic in the morning after fasting for at least 8 hours prior to potassium sample collection.). There is no limit to the number of dose titrations allowed. Subjects will receive up to 12 months of treatment with open-label ZS.

If a patient develops i-STAT potassium values between 3.0 mmol/L and 3.4 mmol/L, inclusive (confirmed by taking a second potassium measurement after a 10 ± 2 minute interval) during the Correction Phase the subject will be directed to not take any more study drug for the remainder of the day and return the next day to continue in the study. E.g. Patients with potassium values between 3.0 mmol/L and 3.4 mmol/L on Day 2 will not take the drug the rest of the doses on Day 2, and will return fasting to have their potassium tested again on Day 3 and continue their therapy. If the potassium has normalized, the patients will start Maintenance Phase from the day. If patients with potassium values between 3.0 mmol/L and 3.4 mmol/L on Day 3, the patients will not take the drug the rest of the doses on Day 3, and will return fasting to be assessed for entering into the Maintenance Phase on Day 4.

Patients with i-STAT potassium <3.0 mmol/L (confirmed by taking a second potassium measurement after a 10 ± 2 minute interval) should discontinue from therapy.

